## 7.3 Data Collection

### 7.3.1 CRFs

Study monitoring data, including information about eligibility and monitoring untoward effects, will be collected on CRFs. CRFs will be completed electronically through iDataFax. All CRFs will be distributed to study staff through iDataFax.

### 7.3.2 Electronic Surveys

Self-administered surveys at Baseline, 3, 6, 9 and 12 month virtual visits will be completed by participants on personal devices via surveys hosted on a secure electronic platform. Data collected using electronic surveys will remain confidential and be stored on a secure electronic platform, accessed by an application programming interface (API) to populate the eP app and administrative portals. The platform API is linked to the eP app allowing participants to take survey's on their personal devices. SID will be used in order to link the interview responses to the participant's CRF data.

The survey will be an embedded webpage, hosted on the study's electronic survey platform, which appears to participants to be a seamless component of the eP app. The survey will be split into multiple modules to ease participant burden imposed by long surveys.

### 7.3.4 Data Security

#### Electronic Survey Data Security

Utilizing a role-based standard, authorized users will be granted unique login names and passwords to access survey data on the survey platform servers. To ensure data privacy, as soon as data is entered (in real-time), it will be encrypted during transmission to the Adolescent Medicine Trials Network for HIV/AIDS Interventions (ATN) Analytic Core (AC) using Secure Socket Layer (SSL) technology. When downloaded, the data is stored in a secure database on an AC server within the AC data center. SSL encryption will be used for transfers of information online and data will be stored in the secure, HIPAA-compliant servers of SurveyGizmo. The Emory AC team maintains a business partner HIPAA agreement with SurveyGizmo.

#### Participant management system data security

The ePrEP participant management system has two components: a back-end "office" that is an interface for administrators and clinicians to manage participants and store data, and a participant-facing mobile app called eP. Emory University holds Business Associate Agreements (BAA) with all components interacting with the app and hosting servers including Microsoft Azure, Zoom, and SurveyGizmo to ensure HIPAA compliance.

The back-end office participant management system, hosted in the cloud, interacts with a custom, secure API developed to communicate data to and from the server. It also interacts with a HIPAA-compliant video conferencing service, Zoom. Both connections are over a secure connection. The cryptographic algorithm the ePrEP participant management system uses is the AES 256 algorithm, with the key hardcoded on the server side. The system uses SSL to communicate with the API. The key size is 128 bits. The system only includes API authentication; there is no other hard-coded information that exists within the system.

Users and devices will be authenticated through the eP app using form authentication through a unique user ID and password, or through login authentication that uses ID and password settings from Facebook or Google. The app will provide no data to Facebook/Google, and vice versa; instead the app will simply use the Facebook/Google system to authenticate the appropriate user to allow for log-in to the eP app. Once an authentication system is established, the eP app will allow users to log in with TouchID if it is enabled on their phone.

All relevant compliance requirements are met by the eP app, including HIPAA compliance, and security measures for personal health information including auto log out feature. All API's for the eP application are HIPAA compliant. Sensitive data including participant's demographic information (name, phone number, and email address) will be accessible in the application. The participant management system stores lab results as an encrypted database within the central Structured Queried Language (SQL) server that is secure and accessed only via authenticated administrators and clinicians. SQL is a programming language that manages data contained in relational database management systems. The lab results will not be stored in the participant mobile facing application.

### 7.3.5 Zoom Platform Description

For the telemedicine consultations conducted through the eP application, the study will rely on the Zoom platform. Zoom will be embedded into the eP app. Participants will use it to communicate with their ATN site study clinician in face-to-face video chat, and text based conversation. Our implementation of Zoom is HIPAA-compliant, and Emory University has entered a Business Associate Agreement (BAA) with Zoom. Zoom includes the following functions to protect users: End-to-End encryption, connects automatically using udp and tcp port 8801, 8802, and 8804 or HTTPS (port 443/TLS), encryption with the Advance Encryption Standard (AES) 256-bit algorithm. Session keys are generated with device unique hardware ID to avoid data being read from other devices. This ensures that the consultation cannot be eavesdropped or tampered with.

## 7.4 Data Submission

### 7.4.1 CRFs

Electronic CRFs in iDataFax will be used to collect key study data (e.g. randomization assignment) and to record study milestones such as study discontinuation, PrEP discontinuation and restarting, clinician decisions regarding PrEP, referrals, and adverse events (AE). AC staff will work with study investigators and the Management Core (MC) to develop CRFs.

### 7.4.3 Survey Data Transmission

Only authorized users, based on correct login, will be able to access and open the study surveys. To ensure data privacy, as soon as data is entered (in real-time), it will be encrypted during transmission to the AC using Secure Socket Layer technology. The data will then be immediately stored in a secure database on an AC server within the AC data center.

#### 7.4.4 Retention Data

Study staff will track participant scheduling and retention through the administrator portal of the ePrEP system. All retention data will be stored in the cloud through HIPAA compliant Microsoft Azure. Access to this database requires user permissions and secure log in. Incremental backups of the entire database are performed regularly to create database redundancy.

#### 7.5 Data Quality Assurance

Investigators receiving federal funding must adhere to the Code of Federal Regulations (CFR) to protect research participants and produce reliable study information. Sites participating in research sponsored by the NICHD need to have an internal quality assurance (QA) plan that will identify problems and correct errors in research study records.

#### 7.6 Role of Data Management

The AC will provide instructions concerning the recording of study data on the CRFs, and entry of the data into iDataFax. Electronic survey results will be linked to the ePrEP participant management system back-end office used by study staff. Lab results will be entered into the participant management system back-end office. Only trained study staff will have access to the web portal dashboard and will be allowed to conduct data entry or exports.

#### 7.7 Study Site Monitoring and Record Availability

Site monitors from the MC and AC may visit participating study sites to review a selected portion of the individual participant records, including consent forms, CRFs and supporting source documentation to ensure the protection of study subjects, compliance with the protocol, and accuracy and completeness of records. Regulatory files, as required, will also be inspected to ensure that regulatory requirements are being followed.

The site investigator will make study documents (e.g., consent forms, case report forms) and *pertinent hospital or clinic records* readily available for inspection by the local IRB, the site monitors, the NICHD, the Office of Human Research Protection (OHRP), or the sponsor's designee for confirmation of the study data.

### 8.0 PARTICIPANT MANAGEMENT

#### 8.1 Tracking Participants / Follow-up

All participants will be followed prospectively for 12 months after assignment to the intervention or control conditions. Research assessments, completed at the participant's home, will be identical for intervention and control participants: surveys at 3, 6, 9, and 12 months, and DBS specimen collection and mailing at 6 and 12 months. All participants will be reminded of their upcoming assessments through the study app. All participants will be followed up for study retention regardless of whether they are actively taking PrEP and/or engaged in PrEP care.

Intervention participants will have a 1-month telemedicine consult with the ePrEP site study staff or clinician, providing an open forum to answer questions/concerns, assess side effects, adherence, behavioral risk, symptoms of acute HIV infection or STD, and provide appropriate clinical management. The intervention arm will have home test lab assessments and telemedicine consultations at 3, 6, 9 and 12 months with their ePrEP site study clinician. Participants assigned to the intervention will receive automatic reminders for scheduled ePrEP site study clinician telemedicine consultations.

Control participants will complete surveys at 3, 6, 9, and 12 months, and home DBS specimen collection and mailing at 6 and 12 months. Control participants will be sent electronic reminders to complete their research assessments. Follow-up calls may also be used for participants who need further reminding and additional follow-up.

All study virtual visits have a set window period for the participant to complete. If a participant misses a virtual visit or scheduled follow-up assessment, they will be allowed to continue in the study for the following virtual visits. They will remain on a 12-month study timeline.

## 8.2 Compensation

The study will compensate all participants who complete baseline procedures with \$100. Participants will receive \$50 for completing the baseline survey and eligibility verification steps, and \$50 for sending back the home test kit. Follow-up compensation will be \$40 for electronic-survey completion and \$40 for DBS collection. Individuals who complete the eligibility screener may also receive up to \$10. Participants who refer individuals for the study can receive \$10 incentive for up to 5 referrals for a maximum of \$50.

## 8.3 Intervening on “Social Harms”

All sites have specific policies governing the treatment of human subjects. These policies specify that medical and psychological assistance will be available in the event a participant should require further evaluation or treatment. Participants will be referred to a local clinic that is able to assist the participant further.

While participants will be informed that they may refuse to answer any question at any time, responses or reactions to certain questions may indicate distress on the part of the participants. If at any time during the study, a participant divulges that he or she is at risk for harm, including but not limited to being abused or experiencing violence, if harm is suspected or likely, or if the participant states he or she is suicidal/homicidal, measures will be taken to ensure his or her safety. Reporting will be done as appropriate to the situation and the legal statutes, and referrals will be provided to appropriate support, counseling or treatment resources.

## 8.4 Criteria for Premature Study Discontinuation

Participants may voluntarily withdraw from the study for any reason at any time. No further data collection will occur from the date the decision is made to permanently discontinue the subject from the study. The study investigators also may withdraw participants from the study in order to protect participant or staff safety. Study staff will record the reasons for all withdrawals. Early study discontinuation may occur for the following reasons:

- Participant has a confirmed HIV-positive test

- If the study is terminated prior to its planned end date
- If the study clinician or the PI determines it is in the participant's best interest to discontinue participation in the study
- If a participant threatens study staff

Any unexpected adverse events that meet the new safety information reporting criteria will be immediately reported to the UNC-CH IRB and the respective sites' IRBs if applicable. Study staff will complete a Study Stop form for participants who are discontinued. This form will include the date, last virtual visit completed, and reason for study discontinuation.

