### 5.5 Laboratory Procedures

All study lab tests will be conducted at CLIA-certified laboratories using FDA-approved tests. Participants will self-collect whole blood in microtubes from finger prick for creatinine and syphilis (using antibody test with reflexive RPR) tests. Whole blood collected on dried blood spot (DBS) cards will be used for HIV testing. Pharyngeal swabs, rectal swabs and a urine sample will be collected for gonorrhea and chlamydia testing. Hepatitis B surface antigen will be tested either through Quest/LabCorp, local health department, or self-collect. Participants may be referred to local testing services, if needed. The Alabama Department of Public Health, Georgia Department of Public Health, Mississippi State Department of Health, and the North Carolina Department of Health and Human Services will be notified of confirmed positive results in accordance with state public health reporting laws, a procedure that will be explained to participants at consent.

*Baseline testing:* All participants will be tested for HIV, syphilis, creatinine, gonorrhea, chlamydia, and Hepatitis B.

*Follow-up testing:* Intervention participants will be tested for HIV, syphilis, gonorrhea, and chlamydia quarterly. Creatinine will be tested at months 3 and 9. All participants are scheduled to return DBS cards for TFV-DP testing at months 6 and 12.

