## 10.0 STATISTICAL/ANALYTIC CONSIDERATIONS

### 10.1 Introduction

10.1.1 A total of 240 participants will be enrolled at baseline to account for a 20% expected loss to follow-up during 12-months of study follow-up.

10.1.2 Primary Outcome: The primary outcome will be detectable TFV-DP drug levels at the month 12 study virtual visit based on an intention to treat analysis. Using standard pharmacological models,[17] TFV-DP level can be used to infer the mean number of days per week PrEP is ingested over a time period of approximately 1-month preceding specimen collection. The cut point used for the primary outcome measure will be TFV-DP levels considered to be a surrogate for substantial HIV protection: >700 fmol/punch, a level indicating  $\geq 4$  doses per week. The intervention efficacy measure will be quantified as the difference in proportions of the intervention arm with this outcome compared to the control arm. For the power calculations, we will therefore use a two-sample comparison of proportions.

10.1.3 Secondary Outcomes: Secondary outcome measures will be harmonized, to the extent possible, with ATN measures. Safety/tolerance outcomes will include: acute HIV symptoms, medication tolerance assessed based on side effects; adherence with number of pills taken in the past week; demographic, socio-economic, and sexual behavioral risk measures derived from the National HIV Behavioral Surveillance (NHBS) instrument and our previous research instruments;[10, 18] PrEP perceptions and PrEP use adapted from the NHBS instrument as well as other sources;[10, 19] commonly used measures for depression;[20] illicit and non-prescription drug use,[21] sexual stigma,[22] HIV severity and risk perceptions,[23] HIV knowledge,[21] medication adherence self-efficacy,[24] the systems usability scale,[25, 26] healthcare coverage,[27] and use of social and geosocial networking sites.[27] We will also seek to understand rationales for those who fail to persist in PrEP, assessing perceptions of PrEP barriers and concerns.[28, 29] The [name] Laboratory may also measure emtricitabine-triphosphate (FTC-TP), which will allow for additional study analyses regarding recency of PrEP dosing.[30]

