## 10.2 Power Estimates

10.2.1 All analyses will assume 80% power to detect a difference at a two-sided 5% significance level. We will also assume a 20% attrition rate in both arms, with independent censoring. Assuming that 5% of participants in the control arm are above cut-point levels of the outcome measure (Section 10.1.2), we will have sufficient power to detect a minimum detectable effect size of 13% absolute difference in the outcome measure (e.g.  $\geq 18\%$  of participants in the intervention arm have outcome measures above the cut-point threshold). A sensitivity analysis determined that to allow for detection of a scenario where intervention outcome level = control+20% absolute increase, our study would remain sufficiently powered with any control participant uptake level  $\leq 15\%$ .

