## 10.3 Statistical Analysis Plan

10.3.1 Aim 1: Analyses of primary outcome that control for potential residual confounding, and analyses of secondary outcomes including initiation of and retention in PrEP care.

Logistic regression and log-linear models will be used to estimate the association between intervention arm and the primary study outcome, TFV-DP level. If prognostic factors associated with the outcome remain insufficiently balanced through stratified randomization, we may adjust for these factors in our models. Potential confounding factors that may be included are medication self-efficacy and motivation to take PrEP. Per protocol assessments that account for potential

changes in intervention as delivered will be conducted. For instance, this would account for participants assigned to the intervention condition opting to instead receive standard of care PrEP from a non-study clinician. A number of secondary analyses will be conducted using regression models. Intervention impact on the secondary outcomes of PrEP initiation and PrEP persistence will be determined using analogous regression models. Another secondary analysis will be to model  $\log_{10}$  (TFV-DP levels) as the outcome variable. An additional secondary analysis will account for changes in PrEP eligibility over time, per CDC guidelines. This has the potential to detect significant smaller “sub-clinical” differences in adherence between the intervention and control study arms. Similarly, an analysis with FTC-TP will allow for a more sensitive and sub-clinical assessment of PrEP use. Other specific and aggregate measures of safety including: renal function, HIV incidence, and incident bacterial STI will be assessed.

**10.3.2 Aim 2: Exploratory analyses of intervention effectiveness across subgroups, and analysis of potential mediators of initiation or persistence in PrEP care across both study arms, such as self-efficacy and urbanicity.**

Heterogeneity of the intervention effects across subgroups will be explored, including that of stratification (race), and socioeconomic indicators. Understanding variables associated with success or failure in home care for PrEP will inform future research, and potentially guide clinician recommendations or policy regarding bringing PrEP to scale. For participants who seroconvert during the study, levels of TFV-DP, PrEP persistence, and other clinically-relevant study data will be analyzed.

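### A participant stopped for confirmed HIV has no scoring rule for the month-12 primary outcome, and unequal HIV testing makes such stops likelier in the intervention arm

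*Combined protocol and SAP*

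**What the plan says.** **Study stop.** Section 8.4 lists reasons for which early discontinuation may occur. One is "Participant has a confirmed HIV-positive test". The list covers both arms and is not limited to tests done by the study. Once permanent discontinuation is decided, "No further data collection will occur from the date the decision is made to permanently discontinue the subject from the study".

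**HIV testing after baseline.** Section 5.5 states: "Intervention participants will be tested for HIV, syphilis, gonorrhea, and chlamydia quarterly". Section 8.1 gives control participants only surveys and the month-6 and month-12 dried blood spot (DBS) cards. Section 11.3.2 describes HIV testing for all participants only at study initiation. Section 6.2.2 calls on-study HIV testing quarterly without naming an arm.

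**Primary outcome.** Section 10.1.2 sets it as TFV-DP "at the month 12 study virtual visit based on an intention to treat analysis", with a cut point above 700 fmol/punch, and says the level reflects roughly the preceding month of dosing. Under 5.5.5, a participant with an initial positive test is told to stop PrEP.

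**Missing values.** Section 10.5 analyses complete cases when few values are missing and mentions imputation only for secondary analyses. Section 10.2.1 states: "We will also assume a 20% attrition rate in both arms, with independent censoring".

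**Seroconverters.** Section 10.3.2 promises: "For participants who seroconvert during the study, levels of TFV-DP, PrEP persistence, and other clinically-relevant study data will be analyzed".

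**The concern.** Whether a participant contributes a primary outcome can depend on an event after randomisation that is linked to the outcome. The chance of detecting that event differs by arm.

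An intervention participant found positive at month 3, 6 or 9 may be stopped and then give no month-12 card. A control participant with the same infection has no scheduled test to reveal it. He is more likely to stay in follow-up, return the card and be counted.

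If the stopped participants are then left out, likely failures leave the intervention denominator more often than the control denominator, and the intervention proportion rises. That is neither intention to treat nor independent censoring.

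The planned seroconverter analysis is affected as well. TFV-DP cards are scheduled only at months 6 and 12, so a participant stopped after a month-3 positive has no TFV-DP value to analyse.

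**Working it through.** **1. The plan's own figure.** Inputs from 3.2 and 10.2.1: 120 per arm, 20% attrition, so 120 × 0.80 = 96 evaluable per arm; 5% against 18%; two-sided 5%; 80% power. With the pooled-variance formula and no continuity correction:

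n = [1.96 × √(2 × 0.115 × 0.885) + 0.8416 × √(0.05 × 0.95 + 0.18 × 0.82)]² / 0.13² = (0.884 + 0.372)² / 0.0169 ≈ 93.4, so 94 per arm.

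94 / 0.80 = 117.5, so 118 per arm or 236 in total, against 240 planned. Power at 96 per arm is 81.1%. The stated figure is reproduced.

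**2. How many could be removed.** The documents give no HIV incidence, so 2 to 6 per 100 person-years is an assumption. A positive at the month-12 visit may come with a card from the same visit, so only the first nine months count:

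- low: 96 × 0.02 × 0.75 = 1.44
- high: 96 × 0.06 × 0.75 = 4.32

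This takes every detected infection as leading to a stop, every stopped participant as a failure, and no stops in the control arm. For a given incidence it is therefore towards the upper end.

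**3. Effect on the intervention proportion.** If k failures leave a denominator of 96, a true proportion p is observed as p × 96 / (96 − k). With p = 0.18, 0.18 × 96 = 17.28:

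- k = 1.44: 17.28 / 94.56 = 18.3%
- k = 4.32: 17.28 / 91.68 = 18.8%

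For whole numbers, with control held at 5%:

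| k removed | Intervention | Contrast |
|---|---|---|
| 0 | 18.0% | 13.0 points |
| 1 | 18.2% | 13.2 points |
| 3 | 18.6% | 13.6 points |
| 5 | 19.0% | 14.0 points |

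A 1-point bias needs 96 − 17.28 / 0.19 ≈ 5 removals.

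**4. How much comes from unequal testing.** With three failures removed from each arm, the contrast is 17.28 / 93 − 4.80 / 93 = 18.58% − 5.16% = 13.4 points. With three removed from the intervention arm only, it is 13.6. So about 0.4 of the 0.6-point inflation comes from dropping failures at all, and about 0.2 from the arm difference.

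**5. False-positive risk.** Exact enumeration of the pooled Z test, with equal true success in both arms and k failures removed from the intervention arm (96 against 96 − k):

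| True rate, both arms | k | Two-sided error | Error favouring intervention |
|---|---|---|---|
| 5% | 0 | 4.3% | 2.15% |
| 5% | 3 | 5.1% | 3.2% |
| 5% | 5 | 5.2% | 3.3% |
| 15% | 0 | 5.0% | 2.5% |
| 15% | 3 | 5.1% | 3.2% |
| 15% | 5 | 5.3% | 3.6% |

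The total error hardly moves. The share favouring the intervention rises by about one percentage point.

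**The case against.** **The stop is discretionary.** A reader might infer from 8.4 that every confirmed infection ends data collection. It does not: the list says when discontinuation may occur, and collection ends only after a decision to stop permanently. That stands. But a case-by-case decision after randomisation is itself a reason to fix the scoring in advance.

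**Both arms are covered.** It is tempting to say failures are removed from the intervention arm alone. The rule also reaches a control participant diagnosed elsewhere, and 6.2.2 names no arm. The documents support less likely detection in the control arm, not its absence.

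**Failure is not certain.** An early seroconverter's month-12 level is simply unobserved. The instruction to stop PrEP and the one-month window make failure very likely, no more.

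**Section 8.1 is not contradicted.** It says: "All participants will be followed up for study retention regardless of whether they are actively taking PrEP and/or engaged in PrEP care". That concerns PrEP use, not HIV status, so an HIV exception can sit beside it.

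**Bias arises only if the analysis drops these participants.** This is correct, and 10.5 is conditional: it recognises that complete-case analysis may mislead. Its remedy, however, is limited to secondary analyses, and a handful of seroconverters is just the situation in which it chooses complete cases. The Safety Monitoring Committee's watch on seroconversion and differential loss (9.0) scores no outcome.

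**The seroconverter analysis is not wholly blocked.** Those found positive at month 6 or 9 were scheduled for a month-6 card, and 10.3.2 also covers PrEP persistence and other data. The loss is partial.

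**Conclusion.** The concern holds as a gap in outcome scoring, made somewhat worse by unequal HIV testing. Followed as written, the plan could drop a few very likely failures, mainly from the intervention arm, in an analysis labelled intention to treat.

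The size is small: about 0.3 to 0.8 points on an 18% intervention proportion, against a 13-point target. Most of it comes from dropping failures at all. The result rests on the assumed incidence, on detected infections leading to a stop, and on complete-case handling. The design claim "All analyses will assume 80% power to detect a difference at a two-sided 5% significance level" is unaffected, and nothing here suggests that the trial's conclusion would turn on this point. The mismatch between 8.4 and 10.3.2 exists whatever the incidence.

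**What to change.** 1. In 10.1.2, state that a participant in either arm with confirmed HIV infection after randomisation stays in the denominator and counts as not meeting the primary outcome, whatever his month-12 TFV-DP value. A level measured after infection no longer describes protection against acquiring HIV, and the score should not depend on whether a stop was applied or a card came back.
2. Report study stops by arm and reason.
3. Reconcile the study-stop and data-collection wording in 8.4 with the TFV-DP analysis of seroconverters in 10.3.2, and 6.2.2 with 5.5 and 8.1 on who is tested for HIV during follow-up. Whether confirmed HIV should remain a stop reason is for the sponsor; the scoring rule works either way.

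**Cost.** Wording only; sample size and power stay as stated. The intervention proportion may be slightly less favourable. Detection remains unequal, so an infected control participant who goes undetected would still be scored on his card. With the same assumed incidence and the plan's 5% control rate, that is at most about 4.32 × 0.05 = 0.2 of a participant counted as a success.
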